Previous studies report that AF is associated with poor health-related quality of life (HRQoL). However, the factors influencing HRQoL in patients with AF are not well understood. A literature review from 2019⁴³ concluded that patients with AF had consistently lower HRQoL than healthy individuals and patients with other cardiovascular diseases. The most common factor associated with HRQoL in patients with AF was anxiety-specific. This may be related to both to the increased burden of disease associated with AF and to fear of complications from treatment.^{44,45} Effects of AF screening on HRQoL is scarcely mapped and highly relevant when considering the benefits of population based screening.

Several knowledge gaps still exist regarding risk stratification, effectiveness, implementation and outcomes of screening programs for AF. Evidence on optimal screening methods in terms of accuracy, cost-effectiveness and feasibility is lacking. Identification of individuals to target for AF screening is essential and the optimal approach to risk stratification for screening purposes remain unclear. Impact of AF screening on clinical outcomes such as stroke prevention, mortality reduction, cognitive function and quality of life is not fully understood and more evidence is needed to assess the long-term effects on patient outcomes, including potential harms associated with overdiagnosis and overtreatment. Subclinical AF refers to episodes of atrial arrhythmia that are asymptomatic and may only be detected through continuous monitoring. It's unclear whether the detection and treatment of subclinical AF lead to improved outcomes compared to clinical AF or if it carries a similar risk of complications such as IS.

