1.3. RESEARCH QUESTIONS AND HYPOTHESES, THEORETICAL APPROACH AND METHODOLOGY

The significance and originality of the proposal:

We propose to perform a randomized controlled screening trial within the Tromsø 8 population-based cohort study, applying monitoring of heart rhythm with leading sensor technology (ECG247) in participants with elevated levels of NT-proBNP. We will add important data to ongoing screening trials by including comprehensive clinical assessments of included subjects. The overall aim of the project is to assess the primary hypothesis that continuous ECG-monitoring in individuals with elevated NT-pro-BNP and subsequent anticoagulant treatment according to current international guidelines leads to reduced incidence of the composite outcome ischemic stroke and cardiovascular death.

The work performed by the PhD student for which we seek funding by this application will create new knowledge related to:

- 1) the age and sex specific prevalence of various burdens of AF (duration, frequency, heart rate and symptoms) and association with repeated measured risk factors in the Tromsø Study
- 2) the association between AF and echocardiographic parameters
- 3) the association between AF, findings on brain MRI and results of cognitive tests
- 4) participants perception of health-related quality of life before and after AF detection by continuous ECG monitoring

The specific research questions which will be addressed in the present PhD project are:

Question 1: What is the age and sex specific prevalence of paroxysmal AF (considering duration, frequency, heart rate and symptoms) and its association with repeated measured cardiovascular risk factors among Tromsø Study participants with elevated levels of NT-Pro-BNP?

Question 2: Can the presence and burden of AF (duration, frequency, heart rate) in the general population with elevated level of NT-ProBNP be predicted by comprehensive echocardiographic evaluation?

Question 3: Is atrial fibrillation associated with cognitive test performance in subjects with elevated NT-proBNP and is this association modified by specific MRI findings?

Question 4: Does detection of AF by continuous ECG monitoring influence health related quality of life?

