The project is planned as a randomized controlled screening trial within the 8th survey of the Tromsø Study (T8), which will be ongoing from March 2025 through 2026. All participants will be invited to complete a questionnaire covering lifestyle, HRQoL, risk factors, as well as simple clinical examinations such as height, weight, ECG, blood pressure, and blood tests. Subsets of up to 10 000 participants will be invited to a second visit to undergo more comprehensive examinations, including extended blood tests with NT-proBNP measurements, cognitive tests, MRI of the brain, and echocardiography of the heart. In the planned trial we aim to include 4000 individuals with NT-proBNP above median without previous known AF or ongoing anticoagulant treatment. Participants will be randomized 1:1 to continuous ECG monitoring using the Norwegian produced ECG247 sensor. ECG247 is an efficient, user-friendly and cost-effective continuous ECG monitor approved for both self-testing and use in health care settings.⁴⁸ The sensor is connected to the

individual participants' smartphone (Bluetooth technology) and has a flash storage if the smartphone is not available. Single lead ECG data is sent to a cloud-based server intermittently. The

Figure 1: Illustration of ECG247 practical setup, modified from www.ecg247.com

system stores information of ECG quality and is evaluated by trained algorithms which classify arrhythmias based on current criteria. The stored data is easily available for the research group, and interpretation, validation, and reclassification if needed. The system fulfills all regulations for a screening tool, as well as handling of sensitive data. Immediate feedback based on an AI based algorithm for analysis will be provided via an app on the participant smartphone if heart rhythm disturbances are detected.

ECG247 has been shown to have

at least as good diagnostic accuracy for AF and improved user-friendliness compared to conventional Holter technology, enables long-term monitoring and can improve the detection of AF.⁴⁸ In most cases, the interpretation is simple and can be performed by other professionals than cardiologists.⁴⁹

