ventricular arrhythmias, SA/AV-block, and other arrhythmias), timing, duration, heart rate of arrhythmias, symptoms and duration of the heart rhythm recording. All study participants will receive information about the test results. A new assessment of HRQoL and medication is planned 6 months post intervention. Initiation and adherence to anticoagulation therapy will be assessed both by questionnaires and by linkage to the Norwegian Prescription Register. Incidence of stroke, cardiovascular and all-cause mortality will be obtained from the Tromsø Study through linkage to national registries.

Safety: In the event of clinically relevant arrhythmias, participants will be contacted as soon as possible. Feedback to the participants will be provided by specially trained physicians and nurses. Participants diagnosed with cardiac arrhythmia or other cardiac abnormal findings will receive advice on follow-up with their general practitioner or be referred to a cardiologist depending of type of arrhythmia. Anticoagulation therapy and other treatments will be recommended if indicated according to current guidelines. The study centre will assist participants who need help to book an appointment for further assessments in cases where this is necessary. An information video about AF will be made in collaboration with the National Association for Heart and Lung Diseases (LHL) to provide general information about AF and potential benefits and risks related to anticoagulant treatment.

Definition of outcomes and other variables of interest: Definition of AF outcome for research question 1 and 2: Paroxysmal AF will be defined as the presence of AF episodes ≥ 30 seconds. In addition, we will register total time in AF (AF burden), beats per minute and concomitant symptoms. Similarly, other tachycardias as atrial flutter (≥ 30 seconds), supraventricular and ventricular tachycardias (cut-offs ≥ 15 seconds and 5 complexes) will also be registered. Initial evaluation will be performed by specially trained research nurses. All positive findings and a similar number of negative tests will be evaluated by a blinded end-point committee of three experts. In case of disagreement the majority will define classification of the outcome.

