Cognitive test performance outcome for research question 3: Scores on the 12-word immediate recall test, the digit symbol coding test and the Mini-Mental State Examination (MMS-E). AF outcomes will be as for question 1 and 2. “Health related quality of life (HRQoL)” outcome for research question 4: A single summary index value (utility score) using a predefined scoring algorithm of the HRQoL EuroQol-5 Dimension (EQ5D) and health anxiety using the Whiteley Index. EQ5D is a standardized instrument developed by the EuroQol group to measure HRQoL and consists of two parts a descriptive system comprising five dimensions (mobility, self-care, usual activities, pain/discomfort and anxiety/depression) and visual analog scale measured ranging from 0 to 100 where patients rate their perceived health status, with 0 being "worst imaginable health state" and 100 being "best imaginable health state." Whiteley Index consists of 14 items, and participants respond on a scale from "not at all" to "very much" or similar gradations.

Relevant echocardiographic variables are atrial size (LAVI, Left Atrial volume Index) and atrial strain (LA reservoir strain). Relevant MRI measures are global and segmental atrophy, volume of white matter lesions, size, presence and number of clinical and subclinical infarcts and micro hemorrhages.

Statistics and analyses: The associations between the primary outcome defined as AF presence(yes/no) and AF burden (number of hours with AF) and prespecified risk factors (traditional CVD risk factors and novel echocardiographic measures) will be examined using multiple regression analyses taking repeated measures within individuals into account by the use of generalized linear mixed effect models and linear mixed effect models, respectively. Linear and logistic (binary or ordinal) regression models with adjustment for relevant confounders will be chosen as appropriate when examining the cross-sectional associations between cognitive test performance and HRQoL outcomes and AF depending on the type of outcome variable (continuous, dichotomous or ordinal). Incidences will be reported as the number of events per 100 years at risk. Censoring for the composite outcome will be done at an event, death of other cause or end of follow-up. Hazard ratios (HRs) will be obtained by Cox regression with adjustment for relevant cofactors. Suitable statistical software will be used for analyses and an experienced statistician will be consulted.

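### Question 4 asks about HRQoL before and after AF detection, but the only stated HRQoL analysis is cross-sectional

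*Protocol*

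**What the plan says.** All of the planning for this question is in protocol section 1.3.

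- **Aim.** Aim 4 is to study "participants perception of health-related quality of life before and after AF detection by continuous ECG monitoring". Question 4 then asks: "Does detection of AF by continuous ECG monitoring influence health related quality of life".
- **First measurement.** In the T8 survey, "All participants will be invited to complete a questionnaire covering lifestyle, HRQoL, risk factors" and other items.
- **Second measurement.** "A new assessment of HRQoL and medication is planned 6 months post intervention".
- **Instruments.** The outcome for Question 4 is a summary index from "the HRQoL EuroQol-5 Dimension (EQ5D) and health anxiety using the Whiteley Index". No time point or change score is named.
- **Analysis.** Under Statistics and analyses, linear and logistic models "with adjustment for relevant confounders will be chosen as appropriate", and the purpose given for them is to be used "when examining the cross-sectional associations between cognitive test performance and HRQoL outcomes and AF depending on the type of outcome variable".

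**The concern.** The aim is about change and its cause, and the design provides a measurement on each side of detection. The stated analysis relates HRQoL to AF at a single time. That suits Question 3, which asks only whether AF and cognition are associated. It does not suit Question 4.

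Participants with and without detected AF are not randomised groups and may differ in HRQoL before anyone is told a result. A cross-sectional gap contains both that difference and any effect of detection. If the first were read as the second, screening would be charged with a harm that it did not cause. The T8 score is also the obvious source of extra precision in a comparison that rests on a few dozen detected cases.

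**Working it through.** **1. Is HRQoL given a longitudinal analysis anywhere else?**

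| Place in section 1.3 | What it covers | HRQoL included? |
|---|---|---|
| Statistics and analyses, mixed models for repeated measures | AF presence and AF burden as outcomes | No |
| Paragraph before Study population, longitudinal assessments | Risk factors, echocardiography, brain MRI, cognitive tests | No |
| Statistics and analyses, linear and logistic models | Cognition and HRQoL, cross-sectional | Yes |
| Gender perspective | Sex adjustment or stratification | Does not bear on the point |

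The cross-sectional sentence is therefore the only analysis assigned to HRQoL.

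**2. Size.** The protocol has no HRQoL effect size, SD or power statement, so there is no figure to reproduce. What follows is an illustration.

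*Inputs from the protocol (Power estimates):* 2000 in the screened arm; number needed to screen 31, so 2000/31 = 64.5, about 65 detected and 1935 not detected.

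*Assumed:* correlation ρ between T8 and 6-month scores of 0.5 to 0.7; a deficit d of 0.1 or 0.2 SD before detection that remains after confounder adjustment; full response; no true effect of detection; and a cross-sectional model fitted to the 6-month score. The protocol does not state the time point of that model.

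Standard error in SD units: √(1/65 + 1/1935) = 0.126.

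Bias under two patterns for the prior deficit (absolute size):

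| Analysis | Deficit stable at d | Deficit decays to ρd |
|---|---|---|
| 6-month score only | d | ρd |
| 6-month score adjusted for T8 score | d(1−ρ) | 0 |
| Group × time (change) | 0 | d(1−ρ), opposite direction |

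Rejection rate = Φ(−1.96 + bias/SE) + Φ(−1.96 − bias/SE). The SE is multiplied by √(1−ρ²) with baseline adjustment and by √(2(1−ρ)) for change. A range is for ρ from 0.5 to 0.7.

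| Analysis | d = 0.2, stable | d = 0.2, decaying | d = 0.1, stable | d = 0.1, decaying |
|---|---|---|---|---|
| 6-month score only | 35% | 12–20% | 12% | 7–9% |
| Baseline-adjusted | 15–10% | 5% | 7–6% | 5% |
| Group × time | 5% | 12–9% | 5% | 7–6% |

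Example: 6-month score only, d = 0.2, stable, has bias/SE = 0.2/0.126 = 1.59, and Φ(−0.37) is about 0.35.

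**3. Precision when there is no prior deficit.** The detectable difference at 80% power and two-sided 0.05 is 2.80 × 0.126 = 0.35 SD on the 6-month score alone. Baseline adjustment multiplies this by 0.87 (ρ = 0.5) or 0.71 (ρ = 0.7), giving 0.31 or 0.25 SD. The change model multiplies it by 1.00 or 0.77, so it gains nothing at ρ = 0.5.

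**The case against.** **Covariates are detail for a statistical analysis plan.** The choice of adjustment variables can be left to that plan, and the phrase about relevant confounders does not exclude the T8 score. This stands: the absence of a named role for the baseline score would not be a finding by itself. What remains is that the protocol states a type of analysis that conflicts with its own aim. A plan that followed the sentence faithfully would not answer Question 4. It may well be a drafting slip, since the data collection is already before and after.

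**A reader might infer that the protocol itself documents lower HRQoL before detection.** Section 1.1 refers to "the increased burden of disease associated with AF and to fear of complications from treatment". In context that remark most naturally explains the role of anxiety in patients who have AF. Trial participants report no history of AF, and section 1.1 describes subclinical AF as asymptomatic. The documents neither establish a prior deficit nor give its size.

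**A reader might infer that baseline-adjusted regression must be the primary model.** The table above does not support that. Under a stable prior deficit it rejects in 10–15% of trials and group × time in 5%; under a decaying deficit the order reverses. The documents do not say which pattern applies, and the groups are not randomised.

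**The comparison group is open.** No text confines the 6-month assessment to one arm, and section 1.1 also speaks of effects of screening on HRQoL. This stands too: comparing detected with non-detected participants in the screened arm is one reasonable choice, not something that the protocol fixes.

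**Conclusion.** The mismatch is real and stands in the current text: a before-and-after question, two planned measurements, and a cross-sectional analysis. As worded, the analysis cannot distinguish a prior difference from an effect of detection.

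The size of the bias cannot be derived from the documents. Under the assumptions listed, false rejection on the 6-month score alone runs from about 7% (d = 0.1 SD, decaying, ρ = 0.5) to 35% (d = 0.2 SD, stable). With no prior deficit there is no bias, and the loss is precision only: 0.35 SD detectable instead of 0.31 to 0.25 SD with baseline adjustment.

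The point affects a named secondary question and one of the four planned manuscripts. It does not touch the primary composite outcome. It should be corrected because the remedy uses data that the trial already plans to collect.

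**What to change.** In section 1.3, Statistics and analyses:

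1. Restrict the cross-sectional wording to cognition (Question 3).
2. State that Question 4 is analysed longitudinally, using the T8 score and the 6-month score of the same instrument. Either the 6-month score adjusted for the T8 score or a group × time (change) model may be primary, with the other as sensitivity analysis. Say that the two rest on different assumptions about a pre-existing difference.
3. Name the comparison, for example screened participants with versus without detected AF.
4. Confirm whether T8 includes the EQ-5D, the Whiteley Index or both; the text says only that HRQoL is covered. For an instrument without a T8 measure, no before-and-after claim can be made. A measure missing before monitoring cannot be recovered later, so this should be checked early.
5. Record as a limitation that residual confounding between detected and non-detected participants remains under either model.

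The cost is wording and slightly more analysis work. No new data are needed for an instrument that is already in T8.

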AF fulfils most criteria for population screening; a severe and prevalent health problem that can be asymptomatic and for which highly effective treatment exists.²⁵ Systematic rhythm monitoring can enable earlier detection of AF and initiation of anticoagulant therapy.^{26,27} Yet, the cost-effectiveness of AF screening is not settled.²⁸ In the recently published STROKESTOP trial, a strategy with AF screening by TED twice daily for 2 weeks was found to reduce the composite primary outcome (stroke, systemic embolism, bleeding leading to hospitalization and all-cause death) by 4% and the risk of IS by 8%.²¹ In the Danish LOOP study, AF screening with ILR resulted in a three-times increase in the number of AF patients detected and anticoagulation initiated and a 20% reduction in the risk of stroke or systemic arterial embolism during follow-up, which did not reach statistical significance (HR 0.80; 95% CI 0.61–1.05; p=0.11).²⁹ The European Society of Cardiology recommends screening for AF in people >75 years of age and in patients with increased risk of stroke, but gives no clear recommendations for method and frequency.⁷

The CHA₂DS₂-VASc risk score is based on age and traditional CVD risk factors and is currently used to predict the risk of IS among patients with AF and guide initiation of anticoagulant treatment. The score's predictive accuracy is however modest, with a C-statistic of ~0.6 for prediction of thromboembolism.^{30,31} N-terminal pro-B-type natriuretic peptide (NT-proBNP) has emerged as a promising biomarker to improve risk prediction. Previous studies have shown that NT-proBNP is elevated in patients with AF and associated with the risk of stroke.³² Data from several randomized trials showed that adding NT-proBNP to the CHA₂DS₂-VASc score significantly improved the prediction of stroke in patients with AF.³²⁻³⁴

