Power estimates: Power estimates are customized to test the primary hypothesis that continuous ECG-monitoring in individuals with elevated NT-proBNP and subsequent anticoagulant treatment according to current international guidelines leads to reduced incidence of the composite outcome IS and cardiovascular death. According to a previous study performed at Sørlandet⁵⁰ with ECG247 the number needed to screen was 45 to detect one unrecognized case of AF in subjects at risk for stroke. When restricting screening to the population with NT-proBNP level > median the number needed to screen may be reduced to 31³⁶ and even 23³⁵ in an older population. The 6-year risk of the composite outcome is expected to be 4% in the control group. Risk in the group screened where no AF is found varies from 2 to 3%. In the group screened where AF is found the risk is 10% (30% risk of IS during a 6-year period, reduced by 70% with oral anticoagulant therapy). If the 6-year risk among screened participants without AF is 2.2%, and we include 2000 participants in each group, there is 80% power to detect a significant difference ($\alpha=0.05$) between control and intervention groups with estimated risk of 4.0% vs. 2.4% for the composite outcome, respectively. Based on the results of the Loop and StrokeStop study and the younger population in the Tromsø study, we expect to reduce risk of the composite outcome from 4% in the control group to 2.4% in the screening group. Compared to previous epidemiological studies, the planned epidemiological projects for the PhD student will have sufficient statistical power to explore meaningful associations.

Data handling and storage: EUTRO is a research administrative tool that will be used for data collection and storage in Tromsø 8. EUTRO provides a complete overview of a study's total research material, including responses to questionnaires, biological material, health data, and project information. EUTRO is integrated within TSD (services for sensitive data located at University of Oslo) which assures and facilitates anonymized data handling and storage according to present regulations and research needs. All data security is taken care of according to the requirements from the Norwegian Data Protection Authority, and privacy is well maintained in the system. The system ensures compliance with the Health Research Act and GDPR requirements for security, handling, and administration of sensitive research data and biological material.

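### The 80% power rests on a 4.0% control risk that the protocol's own AF yield and risks do not produce; applied to both arms, they give roughly 12–42%

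*Protocol*

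**What the plan says.** All the inputs stand in the power paragraph of Protocol section 1.3.

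- Control arm: "The 6-year risk of the composite outcome is expected to be 4% in the control group".
- Screened, no AF found: "Risk in the group screened where no AF is found varies from 2 to 3" per cent. The calculation then uses 2.2%.
- Screened, AF found: "In the group screened where AF is found the risk is 10% (30% risk of IS during a 6-year period, reduced by 70" per cent by anticoagulation).
- AF yield: in an earlier study with the same device, "the number needed to screen was 45 to detect one unrecognized case of AF". Restricting to NT-proBNP above the median may lower this to 31, and to 23 in an older population.
- Result: "If the 6-year risk among screened participants without AF is 2.2%, and we include 2000 participants in each group, there is 80% power" at alpha 0.05 for 4.0% versus 2.4%.

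The paragraph adds an external justification: "Based on the results of the Loop and StrokeStop study and the younger population in the Tromsø study, we expect to reduce risk" from 4% to 2.4%. Section 1.1 gives the overall results of those two trials. For LOOP it reports "a 20% reduction in the risk of stroke or systemic arterial embolism during follow-up, which did not reach statistical significance". For STROKESTOP, screening "was found to reduce the composite primary outcome (stroke, systemic embolism, bleeding leading to hospitalization and all-cause death) by 4" per cent, and reduced IS by 8%. It also mentions a significant LOOP subgroup effect on stroke above the median NT-proBNP, without its size.

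**The concern.** The screened arm is built as a mixture of people with and without detected AF; the control arm is simply given as 4%. In a randomised comparison both arms must have the same expected share of screen-detectable AF and the same risk in everyone else. Screening can then change the outcome only through the detected cases. A control risk of 4% beside an AF-free risk of 2.2% implies either a very high risk in undiagnosed AF or a benefit to people in whom screening found nothing.

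This is the only justification for 4000 participants and six years of follow-up on the primary hypothesis. If the true power is far below 80%, a non-significant result is the likely outcome even when screening works exactly as assumed. It could then be misread as evidence against NT-proBNP-guided screening.

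**Working it through.** **1. The stated figure.** For a pooled-variance two-proportion test with 2000 per arm and two-sided alpha 0.05, 4.0% versus 2.4% gives 82% power. For 80% power the formula needs 1899 per arm, or 2022 with continuity correction. The stated 80% reproduces.

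**2. Where 2.4% comes from.** Let N be the number needed to screen, r0 the AF-free risk, T the risk in detected, treated AF and U the risk in the same people untreated.

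- Screened risk = (1 − 1/N)·r0 + T/N
- Control risk = (1 − 1/N)·r0 + U/N

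The protocol does not show its derivation. With r0 = 2.2% and T = 10%, N = 45 gives (44/45)(2.2%) + 10%/45 = 2.37%, and N = 31 gives 2.45%. Both match the stated 2.4%.

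**3. The control arm from the same inputs.** With U = 30%:

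| N | Control | Screened | Difference (points) | Power, 2000 per arm |
|---|---|---|---|---|
| 45 | 2.82% | 2.37% | 0.44 | 14% |
| 31 | 3.10% | 2.45% | 0.65 | 24% |
| 23 | 3.41% | 2.54% | 0.87 | 37% |

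The difference is (U − T)/N = 20 points/N, whatever r0 is. Per 2000 screened that is 9 to 17 events avoided, against 2000 × 1.6% = 32 assumed.

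**4. The full span of stated inputs.**

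- T = 10%, r0 from 2% to 3%: power is 12–15% (N = 45), 20–25% (N = 31) and 31–39% (N = 23).
- T = 30% × 0.3 = 9% instead of the rounded 10%: the top rises to 42%.
- Overall: 11.9% to 42.2%.

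**5. What the assumed figures would require.**

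- Control risk 4% with r0 = 2.2%: U = [4% − (1 − 1/N)·2.2%]·N = 83%, 58% or 44% for N = 45, 31, 23.
- A 1.6-point difference at 20 points per case: a yield of 1.6/20 = 8%, or 1 in 12.5, against 2.2–4.3% from N = 45 to 23.
- Control risk does come near 4% when r0 = 3% (3.6–4.2%), but the screened arm is then 3.2–3.3%, not 2.4%.

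**6. Assumptions more favourable to the trial.**

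- *Cardiovascular death added to the untreated risk.* The protocol gives no figure, so U = 35–40% is my assumption. In the best case (N = 23, r0 = 2%) power is 54–68% with T = 10%, and 71% with U = 40% and T = 9%. Reaching 80% with T = 10% and r0 of 2–3% needs U of 45–51% (N = 23), 57–64% (N = 31) or 77–88% (N = 45).
- *10% taken as exactly a 70% reduction.* Then U = 33%, and power is at most 49%.
- *Treatment removes all risk in detected AF.* With U = 30%, T = 0 and r0 = 2%, power is 29%, 51% or 74%.
- *Stated yields dropped, and the AF share solved to make control 4%.* With r0 = 2.2% and U = 30% this needs N = 15.4 and gives a screened risk of 2.7% and power 62%. With r0 = 2% it needs N = 14 and gives 72%.

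**7. The external justification.** The assumed relative reduction is 1.6/4.0 = 40%. The overall results in section 1.1 are 20% (not significant), 4% and 8%.

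**The case against.** The strongest reply is that the protocol never states an untreated composite risk in AF. The 30% is for IS alone, whereas the 10% sits in a passage about the composite and may already include some cardiovascular death. Setting one against the other could understate the effect. That stands as a limit on the exact figures, which is why step 6 raises the untreated risk. The power still stays below 80% until that risk reaches at least 45%, at a yield the protocol ties to an older population while calling the Tromsø population younger.

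The numbers needed to screen come from other studies and are not declared as this trial's yield, and 42% is not a hard ceiling because it depends on rounding. Both points are fair. Yet solving freely for the AF share gives 62–72%, still short of 80%.

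The LOOP analysis above the median NT-proBNP is a closer comparator than the overall trial results and might show a larger effect. Since the protocol gives no size, the reader cannot tell. This part is secondary: the mismatch among the stated risks exists whatever that result was.

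Other treatments may also help participants with other arrhythmias, as the Safety paragraph in section 1.3 allows, but the power text neither quantifies nor uses that route. Finally, the Risks and mitigation paragraph concedes optimism if AF prevalence and event risk turn out lower than expected. The mismatch arises when both are as stated, and the mitigation offered concerns only completion of the thesis.

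**Conclusion.** The concern holds. The power formula is correct, but 4.0% and 2.4% do not come from one set of inputs that two randomised arms could share. On the simplest reading of the protocol's figures (AF-free risk 2.2%, 30% untreated, 10% treated) power is 14–37%; across all stated values it is about 12–42%. None of the more favourable variants in step 6 that keep the stated 30% or 33%, or raise it to 40%, reaches 80%.

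These figures assume two-sided testing, no dropout, the 30% IS risk standing in for the untreated composite risk, every detected case treated and no control diagnosed. The last two favour the trial. The point must be fixed because the stated power for the primary hypothesis is not a property of the design as described.

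**What to change.** Rewrite the power paragraph so that both arms' risks come from one AF-free risk, one AF yield, and a stated untreated and treated risk of the composite (IS plus cardiovascular death) in AF. Replace the single claim of 80% with the resulting pairs of risks and power over numbers needed to screen of 23–45 and AF-free risks of 2–3%; the table in the working is an example at 2.2%. If cardiovascular death or treatment of other arrhythmias is meant to add to the effect, give its assumed size. Either name the LOOP or STROKESTOP result and effect size that supports the assumed reduction, or delete that sentence.

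The cost is one paragraph, with no change in conduct or enrolment, and a much less favourable stated power. The rewrite does not restore power. At 30% versus 10%, 80% power needs about 5,600–7,500 per arm at a number needed to screen of 23, 9,500–12,900 at 31 and 18,600–25,900 at 45. Even the smallest, 2 × 5,600 = 11,200 in total, exceeds the 10,000 people to be invited to the second visit. The protocol should therefore say plainly how a non-significant primary result will be read.
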